### Required Interventions

Participants will be required to take one study vitamin D3 supplement tablet daily for the duration of the study (six months), beginning on the day of their enrollment.

### Prohibited Interventions

Participants are expected to not take the following medications during their participation in the study. If these medications are clinically necessary and prescribed by a provider, the participant may be withdrawn from the study based on the PI's discretion.

- Multivitamins
- Anticonvulsants
- Systemic glucocorticoids
- Antipsychotics
- Antihypertensives
- Vasoactive drugs
- Antilipidemics
- Metformin or other oral insulin regulators
- Chemotherapeutics or other cancer treatments

## 5.4 Adherence Assessment

Adherence to the vitamin D supplement will be measured using MEMS cap, pill count, and the medication calendar log. Each supplement bottle will be equipped with a MEMS cap, which will be activated when the study supplement bottle is dispensed during enrollment. Study staff will assess the adherence measures (MEMS cap, pill count, and medication calendar) during follow-up. To promote valid MEMS cap data, subjects will be advised to take their study vitamin D supplement once daily directly from the dispensed bottle—preferably around the same time each day. Use of other medication storage devices or dispensers will be discouraged.

## 6. STUDY PROCEDURES

### 6.1 Schedule of Evaluations

Assessment	Screening	Enrollment	3-month Follow-Up	6-month Follow-Up
	(Visit 0)	(Visit 1)	(Visit 2)	(Visit 3)
Inclusion/Exclusion Criteria	x			
Informed Consent/Accent Form	x	x		
Demographics	x			
Medical History	x	x	x	x
Anthropometric Measurements	x	x	x	x
Skin Color Assessment	x			x
Short Vitamin D and calcium intake FFQ & Sunlight Exposure Questionnaire	x			x
Blood Chemistries	x	x	x	x
Urine Pregnancy Screen*		x		x
Brachial FMD		x	x	x
Pulse Wave Velocity/Analysis		x	x	x
Dual-Energy X-ray Absorptiometry (DXA) Scan		x		x
Activity Survey		x		x
Youth and Adolescent FFQ		x		x
Pubertal Self-Assessment (Tanner Stage)		x		
Dispense Study Vitamin D Supplement		x	x	
Medication Adherence			x	x

\*Only post menarchial girls require a urine pregnancy screen as a safety requisite for DXA scan

### 6.2 Description of Evaluations

Potentially eligible patients passing the inclusion and exclusion criteria will be screened. Screened participants who are found to be vitamin D-deficient (serum 25(OH)D concentration <20 ng/mL) will be eligible to enroll in the study. Eligible participants will be scheduled for enrollment visit within eight weeks of their screening evaluation. Study duration is six months. Randomized participants will return for follow-up evaluations twice. The first follow-up visit will

occur approximately three months after their enrollment visit, and their final study visit will be scheduled approximately three months thereafter.

## Screening Evaluation

### **Consenting Procedure**

Written informed consent will be obtained separately for screening and for enrollment, at the respective study visits. The parent or medical legal guardian of the child (as defined by state law) will be given a copy of the informed consent and will be provided an opportunity to read the consent in its entirety. For a legal guardian to consent on behalf of a child to participate in research, the guardian must present a copy of the appropriate legal document proving guardianship under state law before signing the consent document. A copy of the guardianship document will be included in the research subject's chart.

The consent form given at the screening visit will describe the procedures that will take place only during the screening visit. The consent form given at the enrollment visit will detail all procedures to be performed at each study visit. Participants must give their assent and only biological parents, or legally-recognized guardians, may provide consent.

Only trained study coordinators and the principal investigator may obtain informed consent from participants. Person obtaining consent will review all aspects of the consent and allow the parent or legal guardian the opportunity to ask questions. The following points will be explained to the parent(s) or legal guardian(s) at the time of consent:

- The study involves research
- The purpose, background and rationale of the study
- Study involves taking vitamin D supplementation (Vitamin D3 600 IU vs. 1000 IU vs. 2000 IU once daily for six months) which has been masked and randomly assigned
- The responsibility of the parent and the participant
- All reasonably foreseeable risks or inconveniences associated with all the expected study procedures (i.e. vascular function tests, DXA scan, blood draw, skin color estimation, completion of physical activity, diet and sun exposure surveys)
- Potential risk of hypervitaminosis D (vitamin D poisoning) and its symptoms
- The expected benefits of the study
- The participation in this study is voluntary and that the parent or subject may refuse to participate or withdraw from the study at any time without penalty or loss of benefits to which he/she may be entitled
- The accessibility of the records to the regulatory authority(ies), monitor(s), auditor(s), or other appropriate reviewers
- Maintenance of confidentiality of the patient record

The consent form will include: the parent(s) or legal guardian(s) signature, the printed name of the child, and the date, as to document that all-of-the-above was completed. Participants who are 18 years of age will sign their own consent. The consenting research staff member will also sign the consent form to indicate that he/she has reviewed and explained the consent form with the subject and was present at the time of signing. After obtaining signed

consent, a copy of an unsigned consent form will be given to the parent(s) or legal guardian(s) for their records. The original signed copy of the consent will be kept within the study folder.

## **Screening**

The following procedures are performed to determine a subject's eligibility:

- *Age Calculation:* To enter the study children should have completed their 10th birthday and not have had their 19th birthday. 18-year-old children are eligible to enroll until the day before their 19th birthday.
- *BMI Calculation:* Height will be measured three times in centimeter (cm) to the nearest 0.1-cm and averaged to determine the participant's height in centimeter. Weight will be measured three times in kilogram (kg) to the nearest 0.1-kg and averaged to determine the participant's weight in kilogram. BMI will be calculated using the following formula:

$$[\text{Weight in kilogram}]/[\text{Height in meter}]^2$$

BMI can also be calculated using metric measurements of height (in cm) and weight (in kg) through NHLBI online BMI calculator available at:

<http://nhlbisupport.com/bmi/bminojs.htm>

- *Medical History Form:* Captures anthropometrics, demographic data (age, sex, race, and ethnicity), level of education, smoking status, current medications, and type of medical insurance.
- *Contact Form:* To be completed by parent unless subject is 18 years of age
- *Vitamin D and Sunlight Exposure Questionnaire:* To be completed by parents unless subject is 18 years of age
- *Waist Circumference Measurement:* Waist circumference will be measured three times, using a non-stretch tape measure, at the mid-point between the lowest rib and the iliac crest at minimal respiration while standing. The respective waist circumference measurements will be measured to the nearest 0.1 cm and averaged.
- *Fitzpatrick Sun-reactive Skin Type estimation:* Sun-reactive skin type estimate will be made by the parent unless the subject is 18 years of age
- *DSM II Colormeter Measurement:* Study staff will normalize the dermatophotopspectrometer on the calibration plate and obtain three readings from the forehead, back of the hand, and inner upper arm. The measurements obtained at each site will be averaged to estimate the melanin index at the respective sites.
- *Venipuncture, Specimen Collection, and Specimen Processing:*
  - *Venipuncture:* Venipunctures at the Primary Care Center will be done by the clinic nurses or phlebotomy-trained medical assistants. For subjects consenting for screening at the Pediatric PittNet practices, venipuncture will be performed by the pediatric PittNet nurse, the clinic nurse, or the phlebotomy-trained medical assistants

- *Specimen Collection:* At least 5 mL of blood needs to be drawn in one or two red-top tubes and 10 mL of blood in one or two green-top tubes
- *Specimen Processing:* Label the specimens with screening ID, date of birth, and date of visit. Complete lab test order forms (instructions for lab procedures). Enclose the collected tubes in a medical-biohazard seal bag with the lab order/procedure instruction sheets and drop-off the specimens at the appropriate place in the UPMC Central Lab building or in the clinic for transportation of the samples to the Clinical Chemistry Lab at UPMC Presbyterian.

## Enrollment

### Enrollment

Participants that are deemed vitamin D deficient (serum 25(OH)D concentration <20 ng/mL) and meet all other inclusionary criteria are eligible to enroll in the study. Prior to entering the study (initiation of baseline assessments and randomization), participants will be required to complete a second informed consent, which outlines the assessments that will take place at the three study visits.

### Baseline Assessments at enrollment

Patients who have been successfully screened for the study and have enrolled will undergo the following baseline assessments:

- *Medical history form*
- *Anthropometric measurements*
- *Venipuncture, specimen collecting, and specimen processing*
- *Urine pregnancy screen:* Only post-menarcheal girls require urine pregnancy screen. Only subjects with a negative pregnancy screen will be permitted to enroll.
- *Fasting glucose concentration screen:* Only participants with fasting serum glucose <125 mg/dL will be permitted to enroll
- *Activity survey:* Participant may complete this survey, with parental help if they are ≤17 years of age.
- *Nutritional survey:* Parent may complete a survey regarding subject's food frequency habits for participants ≤17 years of age. If subject is 18 years of age or older, he or she will complete this questionnaire on their own.
- *Pubertal self-assessment:* Subjects will self-identify their pubertal stage by looking at Tanner Stage drawings and selecting the image that corresponds most closely to their stage of development.
- *Vascular function testing (pulse wave velocity, pulse wave analysis, and flow mediated dilation, and blood pressure measurements)*
  - *Blood pressure.* Measurements will be obtained by a CTRC vascular technician prior to vascular health assessments, and after 10 minutes of participant rest and acclimatization while supine, using a model CONTEC08A automated digital oscillometric device (cuff 22-32 cm). Measurements will be taken three times, one minute apart, and averaged.

- Endothelial function. Brachial artery diameter will be measured using a high-resolution ultrasound machine (GE, Vivid 7, GE Health care, Milwaukee, WI) equipped with a 9-L linear transducer preset to a dedicated vascular scanning protocol. We will then occlude brachial arterial flow at the upper forearm using a 5-cm-wide occlusive cuff (Hokanson SC5) inflated to a pressure of 50 mmHg above the systolic blood pressure or to 200 mmHg, whichever is greater, by a rapid release sphygmomanometer (Hokanson DS 400) for 5 minutes. Post-cuff release diameter measurements during the reactive hyperemic phase, obtained at 60, 120, and 180 seconds, will be used to calculate FMD%.
- Arterial Stiffness Indices. Carotid-femoral pulse wave velocity (PWV), Aortic Augmentation Index at heart rate of 75/min (Alx-75), and central systolic and diastolic blood pressure were measured using arterial tonometry (SphygmoCor CVMS V9, CPVH System, Model EM3, AtCor Medical, Sydney, Australia).
- *DXA scan:* Measures total body adiposity and percent of body fat

Participants should enroll within two months of initial screening. If participants do not enroll within this time window, they will be required to rescreen to ensure eligibility. Subjects that have successfully completed the enrollment process and baseline procedures will be randomized to a study intervention dosage, which is blinded to both study team and participant.

Parents will be instructed to record each dose of intervention given to their child in a calendar supplied by the investigators.

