**Design and Outcomes**

In a double-blinded, controlled trial, we propose to randomize 229 eligible children to receive either 600 IU (conventional supplementation, current recommended dietary allowance), or 1000 IU or 2000 IU (enhanced supplementation) of vitamin D3 daily for six months.

The primary outcome measure will be change in brachial flow-mediated dilation percentage at 6 months (FMD%); FMD% is a measure of vascular endothelial function. The secondary outcome measures will include (1) pulse-wave velocity (PWV) – a measure of arterial stiffness, (2) central and systemic blood pressure, (3) fasting blood glucose concentration, (4) 1/fasting insulin concentration as a surrogate for insulin resistivity, (5) lipid profile indices, (6) adipocytokines (plasma leptin, and adiponectin) and systemic markers of inflammation (plasma high-sensitivity CRP, IL-6, TNF- $\alpha$ ).

Eligible participants will be scheduled for enrollment within eight weeks of the initial screening visit. Follow-up visits will occur approximately at three months and six months after enrollment. FMD%, PWV, biochemical measurements, and inflammatory markers will be obtained at each study visit; DXA scan will be done at enrollment and at 6 months.

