**Sample Size and Population**

We aim to enroll 229 otherwise healthy 10- to 18-year-old, overweight (BMI percentile,  $\geq 85^{\text{th}}$  to  $< 95^{\text{th}}$ ) or obese (BMI percentile,  $\geq 95^{\text{th}}$ ), vitamin D-deficient (serum 25(OH)D concentration <20 ng/mL) children.

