#### **4.1 Inclusion Criteria**

Potentially eligible children will be

- 10 to 18 years of age
- otherwise healthy
- obese or overweight (BMI  $\geq 85^{\text{th}}$  percentile)
- able to understand all aspects of study procedures
- able to voluntarily comply with all study procedures across the duration of the study
- vitamin D-deficient and normocalcemic during screening (serum 25(OH)D concentration  $< 20$  ng/mL; serum calcium concentration: 10-14 years, 8.8-10.8 mg/dL;  $\geq 15$  years 8.4-10.2 mg/dL)

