#### **Secondary outcome**

Our secondary outcomes will include: (1) pulse wave velocity (PWV) as a measure of arterial stiffness, (2) 1/ fasting insulin concentration as a surrogate for insulin sensitivity, and (3) metabolic syndrome risk factors (blood pressure, waist circumference, HDL cholesterol, triglycerides, and fasting blood glucose) at the 6-month follow-up.

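### Only a 22-32 cm blood pressure cuff is named for overweight and obese 10- to 18-year-olds, with no arm measurement and no rule for arms outside that range

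*Combined protocol and SAP*

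**What the plan says.** The blood pressure procedure is in section 6.2 of the combined protocol and SAP, under Baseline Assessments at enrollment. It fixes the operator, the rest period, the supine position, the device and the cuff: "using a model CONTEC08A automated digital oscillometric device (cuff 22-32 cm". On replication it says "Measurements will be taken three times, one minute apart, and averaged". The same vascular testing is repeated at 3 and 6 months.

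Section 4.1 admits children who are "obese or overweight (BMI" at or above the 85th percentile). Sections 4.1 and 4.2 set no ceiling on BMI, weight or arm size. Section 6.2, under Screening, adds that "18-year-old children are eligible to enroll until the day before their 19"th birthday.

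The body measurements described there are height, weight and waist ("Waist circumference will be measured three times, using a non-stretch tape measure"). Arm circumference appears nowhere.

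Blood pressure is an outcome in two places. Design and Outcomes lists "central and systemic blood pressure", and section 9.4 lists "metabolic syndrome risk factors (blood pressure, waist circumference, HDL cholesterol, triglycerides, and fasting blood glucose) at the 6-month follow-up". Section 9.5 analyses the secondary outcomes with mixed models of change over baseline, 3 and 6 months, and also tests treatment effects at 3 and 6 months.

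**The concern.** The trial selects children for high body size and then names a cuff whose stated range stops at 32 cm. Arms above 32 cm are foreseeable in such a sample, particularly among the older and heavier adolescents. The text gives staff no second cuff and no instruction for such an arm. Because arm circumference is not recorded, nobody could tell afterwards which readings came from outside the range.

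An error from cuff fit is systematic within a child, so averaging three readings does not remove it. Three things are at stake:

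- the blood pressure levels that the trial reports;
- the precision of any comparison of 6-month levels;
- the measured change in a child whose arm grows past 32 cm, or shrinks below it, during the six months.

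**Working it through.** **Inputs from the documents.** One cuff range, 22-32 cm (6.2), which I read as arm circumference although the text does not say so. 56 children per arm at the end of the trial, and 89% power for secondary outcomes at effect size 0.61 (9.2). Two-sided α = 0.05 for secondary outcomes (9.5). Allocation 1:1:1 and blinded (9.1).

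**Inputs not in the documents.** The arm-circumference distribution, the blood pressure SD, and the size and direction of error from an ill-fitting cuff. All figures for these are assumptions.

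**Step 1. Reproduce the plan's own figure.** With n = 56 per arm, d = 0.61 and α = 0.05, the noncentrality is 0.61 × √(56/2) = 3.23. The noncentral t gives 89.2% and the normal approximation 89.8%, in line with the stated 89%. This figure does not depend on the cuff.

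**Step 2. Share of arms above 32 cm (assumed distributions).** Share = 1 − Φ((32 − mean)/SD).

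| Assumed mean arm (cm) | SD 4 | SD 5 |
|---|---|---|
| 30 | 31% | 34% |
| 33 | 60% | 58% |
| 35 | 77% | 73% |

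These means may be too high for a sample that starts at age 10 and the 85th percentile, so the next steps use a share p of 10-50%. The noise in step 4 depends on p(1 − p), which is largest at p = 0.5, so that range includes the worst case for noise.

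**Step 3. Shift in reported levels.** With a constant error b of 3-10 mmHg in the affected children, the mean shifts by p × b. That is 0.10 × 3 = 0.3 mmHg up to 0.50 × 10 = 5.0 mmHg, the same in expectation in every arm. At the largest share in step 2 it would be 0.77 × 10 = 7.7 mmHg.

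**Step 4. Noise in a comparison of 6-month levels.** With a true SD of 10 mmHg, the observed SD is √(100 + b²p(1 − p)).

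- p = 0.10, b = 3: √(100 + 0.81) = 10.04. A 6.1 mmHg difference is d = 0.608, and power is 89.0%.
- p = 0.50, b = 10: √(100 + 25) = 11.18. The same difference is d = 0.546, and power is 81.6%.

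**Step 5. Bias between arms.** The expected bias is b × (p₁ − p₀), where p₁ and p₀ are the shares affected in the two arms. Under randomisation this is zero. Chance imbalance gives it an SD of b × √(2p(1 − p)/56): 3 × √(0.18/56) = 0.17 mmHg up to 10 × √(0.50/56) = 0.94 mmHg. Step 4 already counts this variation, so the two should not be added.

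**Step 6. Change from baseline.** If the error is b at every visit, change = (true₆ + b) − (true₀ + b) = true₆ − true₀, and the error cancels. If the arm crosses 32 cm between visits, that child's change carries the whole of b, here 3-10 mmHg. The documents do not allow an estimate of how many children cross.

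**The case against.** The strongest reply is that the protocol names a cuff range without excluding others. Section 10.2 also promises an operation manual to standardise measurements, and such a manual could hold a cuff-selection rule. This stands as far as it goes: use of one cuff for every child is an inference. But the promise is general and says nothing of cuffs, while the procedure itself is otherwise specific. Following the written text means using the 22-32 cm cuff on every arm.

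The second reply is that blinded randomisation and a change-based mixed model remove most of the harm. This largely stands, and steps 5 and 6 show why. It does not cover reported levels, the tests at 3 and 6 months in so far as they rest on levels, or arms that cross 32 cm.

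A reader might also infer more than the documents support:

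- *That blood pressure in the heaviest children is wrong, and reads too high.* The documents give no arm sizes and neither the size nor the direction of any error. They support only that such readings lie outside the stated range and may be biased.
- *That raised blood pressure will be over-counted.* Sections 9.1, 9.4 and 9.5 plan no such count, and no blood pressure cut-off is used for eligibility or safety.
- *That the primary outcome is compromised.* The occlusion pressure for FMD is the greater of systolic pressure plus 50 mmHg and 200 mmHg, so the reading matters only above 200 − 50 = 150 mmHg. The sample size does not depend on blood pressure.
- *That central pressure is affected too.* It is measured by tonometry, and the documents do not link it to the cuff reading.

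**Conclusion.** The point holds as a correctable weakness in how a secondary outcome is measured. It goes beyond missing detail, because applying the stated cuff to a larger arm would itself give a less trustworthy reading.

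The consequences are limited. Reported levels may be shifted, comparisons of 6-month levels gain some noise, and change may be distorted in children who cross 32 cm. No bias between arms is expected, and a constant error largely cancels in change.

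The figures in the working (0.3-5.0 mmHg on levels; power at 0.61 of 89.0% to 81.6% against 89.2%) illustrate scale only. They rest on an assumed share of 10-50%, an assumed constant error of 3-10 mmHg and an assumed SD of 10 mmHg. The zero expected bias rests on randomisation and on the error not depending on dose.

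**What to change.** In section 6.2, replace the bracketed cuff range with: *cuff chosen so that the measured mid-upper-arm circumference lies within its labelled range; circumference and cuff size recorded at each visit*.

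In section 9.5, add that any change of cuff within a child is flagged and that the blood pressure analysis is repeated without those children. This should be a sensitivity analysis only, since it excludes children on something that happens after randomisation.

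Section 9.2 already describes the recruited sample, so many children may have been measured. Without a recorded arm circumference, their out-of-range readings cannot be identified directly. For them, state which cuffs were actually used, run a sensitivity analysis by baseline weight or BMI, and report the limitation.

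The cost is one extra cuff and a tape measurement at visits that already include anthropometry (section 6.1). The downside is that choosing the cuff at each visit can itself change the instrument within a child, which is why cuff size must be recorded.

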### 3-month Follow-up Visit

The window for the follow-up visit will be three months after the enrollment date ( $\pm 15$  days). The following procedures will be performed at this visit:

- Medical history form
- Anthropometric measurements
- Venipuncture, specimen collecting, and specimen processing
- Vascular function testing (pulse wave velocity, pulse wave analysis, and brachial flow mediated dilation, and blood pressure measurements)
- Medication adherence assessment
  - Collect medication calendar
  - Read MEMs cap and obtain Patient Adherence Report
- Dispensation of second supply of vitamin D supplements

